## 2) INTRODUCTION

This is a feasibility study to investigate the effectiveness of a prehabilitation programme for live renal transplantation donors and transplant recipients. Participants will undergo a 6 week, at home exercise programme prior to their procedure. This programme of prehabilitation will be monitored using an exercise diary and wearable technology. The data will be utilised, along with participant feedback to assess their compliance and physiological effects of the exercise regimen.

This study will inform the research group on the feasibility of bespoke prehabilitation pathways in transplantation, and how digital technology can inform this. The results of this will inform the grant application of a much larger study into the effects of prehabilitation in transplantation.

## 3) BACKGROUND

Prehabilitation programmes have been shown to have significant benefits for patients undertaking surgery in cardiothoracic, general and orthopaedic surgical procedures (1). Benefits include reduction in post operative complications, reduced morbidity and mortality, decreased post operative length of stay (LOS), faster recovery and return to work (1–7). These significant benefits have been found in a spectrum of interventions that concentrate on the three key principles of prehabilitation; exercise, nutrition and psychological support. However, there is a paucity of evidence supporting the use, and demonstrating the feasibility of a prehabilitation programme in transplantation (8).

We already have evidence in other populations that decreased anaerobic threshold is a marker for being high risk for post operative complications (9). Therefore, acting within this period to improve physical fitness is perceived to improve post operative outcomes. Prehabilitation works by acting prior to the insult of surgery to improve a patient's baseline characteristics, such as lean body weight, muscle mass and cardiorespiratory reserve.

Live renal transplantation is an example of one of the most profound altruistic acts in our community. Therefore, it is vital that we optimise all stages of this journey, both in terms of preparation and post operative recovery of the recipient, and importantly for the donor. The aim of this would be to increase satisfaction, reduce post operative LOS, reduce time to being back to work (particularly for the donor who has no baseline medical condition prior to the surgery), and reduce post operative complications.

Not all prehabilitation interventions have shown improvement in their study populations. There are multiple reasons for this, including drop out of exercise programs, or that control groups may significantly benefit from interventions that are meant to act as controls rather than intervention. An example of this includes a prehabilitation study in colorectal cancer that showed no difference between walking and cycling group, but the walking intervention control group did see an improvement in their function from baseline as they also increased their physical activity as part of the study (10). There is also the consideration that patients are not prepared appropriately for the intervention. Asking patients prior to surgery to participate in prehabilitation exercises without understanding the benefits they bring leads to poor compliance (10,11). This is particularly relevant to this study population who may experience post dialysis fatigue, deconditioning and baseline poor mobility (12).

By creating an exercise program that is directly suitable to specific populations, studies have demonstrated this can remove some of the barriers to compliance, as well as leading to improved physical fitness and mental wellbeing (13). In the proposed study the use of electronic vital sign monitors with live feedback of results will act to reinforce the achievement that participants experience by engaging in a pre-surgical exercise plan. There is evidence for the use of wearable technology helping to deliver prehabilitation services in other surgical populations in a similar method that we aim to use (14–16).

Ideally the behavioural change introduced by prehabilitation can be transitioned into the regular lives of patients. This would have a longer lasting impact on patients' health and quality of life (17). This study provides an education and application that can be followed simply in participants own homes and fit around other commitments they have. The patients will be directed by the surgical team as to when physical activities can be restarted post-surgery.

This study will provide key information into how the set-up of the trial and delivery of this service will be met. The study is not powered to detect statistically significant differences in outcome of the two groups, although statistical analysis will be performed to determine whether the impact of this intervention on its participants has led to a measurable change in physiological and clinical outcomes. This study provides the opportunity to test the set-up of a new team, and how the wearable technology can be utilised in this cohort of patients.

We will assess 4 key areas (18). First, we will evaluate the recruitment capability through the transplant team at MRI. This determines the ability and expected speed of recruitment of a much larger study. Secondly, this will evaluate and refine our data collection procedure in terms of data extraction, time for data collection and inform the need for future grants for research staff to be allocated time for OPERATE. Thirdly, this will evaluate the acceptability

and suitability of the intervention. As already discussed, exercise interventions for prehabilitation programmes have struggled previously with finding an acceptable method of exercise intervention, particularly one which participants will remain compliant with. Finally, this will provide a preliminary evaluation of participant responses to the intervention, in terms of improved post operative outcomes and patient satisfaction (18,19). Each of these key areas will provide important actionable information that will lead to a more refined and improved larger study, thereby saving time, funding, and limiting wasteful interaction with participants in the future (20).

### *Funding*

Funding for consumer wearables has been provided by the Kidney for Life charitable fund.

## **4) STUDY OBJECTIVES**

### **4.1 Primary Question/Objective:**

- Is it feasible for renal transplant patients and live kidney donors to participate in a prehabilitation programme in combination with a piece of wearable technology?

### **4.2 Secondary Question/Objective:**

- Are transplant outcomes improved by prehabilitation regimens delivered by video instruction?
- Are there discernible perioperative digital signatures provided by the wearable that link to outcomes?
- Is the quality of perioperative sleep linked to outcomes?

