## 7) OUTCOME MEASURES

This is a feasibility study, the results of which will inform the development and planning of a much larger clinical study into prehabilitation in live renal transplant patients and the use of wearable technology to augment this. The hypothesis is that prehabilitation may have a significant positive impact on the outcomes for recipients and donors in live kidney transplants.

This study will examine the interaction between participants and the prehabilitation exercise videos, the set up for this additional service within the transplantation team and test the methods of data extraction.

This study will perform data analysis which may show benefit of prehabilitation for kidney transplant recipients and live donors, although this is not powered.

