### 9) STATISTICAL CONSIDERATIONS

#### 9.1 Statistical Analysis

##### 9.11 Study analysis

All variables will be explored descriptively with graphs and summary statistics. Key characteristics, such as overall recruitment, compliance with the prehabilitation programme and qualitative analysis of responses to open questions will be used to assess the primary research question.

Description analysis will be performed on all appropriate variables, within the limits of an unpowered study. This will include number (%), mean, median, maximum and minimum values, standard deviation and interquartile range.

The number of potential participants screened, the number enrolled, withdrawals and completion of study will all be listed outcomes.

Qualitative values, such as post operative complications will be listed.

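### The first secondary objective asks whether prehabilitation improves transplant outcomes, but every participant receives it, and the protocol gives lack of power as the only limit

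*Protocol*

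**What the plan says.** The first secondary objective in section 4.2 reads "Are transplant outcomes improved by prehabilitation regimens delivered by video instruction". Other sections use similar language:

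- Section 2: "This is a feasibility study to investigate the effectiveness of a prehabilitation programme for live renal transplantation donors and transplant recipients".
- Section 3: the statistical analysis is to determine "whether the impact of this intervention on its participants has led to a measurable change in physiological and clinical outcomes". The fourth of its key areas is a preliminary evaluation of participants' responses, "in terms of improved post operative outcomes and patient satisfaction".
- Section 5: the opening sentence describes the study as investigating the impact of prehabilitation.
- Section 7: "This study will perform data analysis which may show benefit of prehabilitation for kidney transplant recipients and live donors, although this is not powered".

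The stated caution concerns power each time. Section 3 says "The study is not powered to detect statistically significant differences in outcome of the two groups", section 7 repeats the point in the sentence above, and section 9.11 says "Description analysis will be performed on all appropriate variables, within the limits of an unpowered study". Section 9.2 adds that no power calculation was made.

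On design, sections 2, 5 (Duration) and 5.2 assign all participants the six-week programme. Section 5.1 plans 20 to 40 participants, half donors and half recipients. For post-operative outcomes, section 9.11 says "Qualitative values, such as post operative complications will be listed".

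**The concern.** The objective asks about cause: did prehabilitation make outcomes better? Answering it needs some information on what would have happened without the programme. The protocol provides none for post-operative outcomes, and it does not say so. By giving lack of power as the reason for caution, it suggests that the same design with more patients would settle the question.

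This matters because the results are meant to be used. Section 2 says they will inform a grant application for a much larger study. Section 9.2 says the results and the feasibility findings will indicate the need for, and success of, a later powered study. Under the present wording, a low complication count or a short hospital stay could be carried into that decision as evidence of benefit limited only by sample size.

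**Working it through.** There is no power or sample-size formula to reproduce. The one figure that can be checked is the provisional sample in section 9.2: 10 donors + 10 recipients = 20, which agrees with sections 5 (Duration) and 5.1.

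**1. Who could serve as a comparator?**

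- *Untreated participants:* 0 of 20 at the minimum, 0 of 40 at the maximum.
- *External or historical patients:* none are named. Section 8.3 describes extraction from participants' own records, with consent.
- *The two groups mentioned in section 3:* these are not defined there. The only two groups described are donors and recipients (sections 5.1 and 9.2). Both are treated, so a difference between them says nothing about the programme.
- *Each participant as their own control:* possible for grip strength and wearable measures, which have a baseline (section 5.2). It is impossible for complications or length of stay, which have no value before surgery. Even where a baseline exists, the change is uncontrolled. Section 3 itself cites a colorectal study in which the control group improved from baseline.
- *Higher against lower compliance:* confounded, and narrowed by the rule in section 6.4 that taking part in fewer than 50% of sessions, as judged by the investigator, is a reason for withdrawal.

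**2. Why sample size does not help.** Write the effect as p − p0, where p is the complication rate with the programme (observed) and p0 the rate without it (never observed). The protocol gives no rates, so these are assumed. Take p = 20%.

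| Assumed p0 | p − p0 | Reading |
|---|---|---|
| 10% | +10 points | harm |
| 20% | 0 | no effect |
| 30% | −10 points | benefit |

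Precision of p alone, as the 95% half-width 1.96 × √(0.2 × 0.8 / n):

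| n | Half-width (points) |
|---|---|
| 10 | 24.8 |
| 20 | 17.5 |
| 40 | 12.4 |
| 1,000 | 2.5 |
| 100,000 | 0.25 |

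The half-width shrinks towards zero. The 20-point range for the effect, including its sign, does not move.

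**3. What the design can describe.** These figures show precision only. They use 10 or 20 participants per role (half of 20 or of 40).

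- *Mean within-person change,* half-width t(0.975, n−1)/√n in units of the SD of change: 2.262/√10 = 0.72 at n = 10 and 2.093/√20 = 0.47 at n = 20.
- *Complication rate per role,* exact (Clopper–Pearson) 95% interval:

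| Observed | 10 per role | 20 per role |
|---|---|---|
| 0% | 0–30.8% | 0–16.8% |
| 10% | 0.3–44.5% | 1.2–31.7% |
| 20% | 2.5–55.6% | 5.7–43.7% |
| 30% | 6.7–65.2% | 11.9–54.3% |

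- *A compliance contrast within a role,* which the protocol does not plan, assuming an even split and no withdrawals: half-width t(0.975, 2k−2) × √(2/k) in between-person SDs. This is 2.306 × √(2/5) = 1.46 for 5 against 5 and 2.101 × √(2/10) = 0.94 for 10 against 10. More patients would narrow it but would not remove the confounding.

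**The case against.** The strongest reply is that this concerns wording in a study that calls itself a feasibility study. A single treated group is a normal choice for such a study. The quantitative analysis is descriptive, complications are only listed, and section 9.11 ties the primary question to recruitment, compliance and qualitative responses. The outcome language is partly hedged: section 3 calls the evaluation preliminary, and section 7 says only that benefit may be shown. Change in physiological measures can properly be described, because baselines exist. No section makes the next study depend on a favourable post-operative result, or says that it will lack a control group.

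Most of this is fair, and it limits the point. The design is not at fault, the feasibility conclusions stand, and the harm is a risk of misreading rather than a certainty. It does not answer the core. The hedges never mention the missing comparator, and feasibility status explains a small sample without making an effect identifiable. That the analysis is descriptive means it cannot answer the objective as set.

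Only the protocol was available, so an external comparison planned in a separate analysis plan cannot be excluded. A comparator is, however, a design matter that belongs in the protocol.

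**Conclusion.** The concern holds. The first secondary objective, and the matching statements in sections 3 and 7, ask for an attribution that this design cannot support for post-operative outcomes. With 0 of 20 or 0 of 40 participants untreated and no outside comparator named, the obstacle is identifiability, and lack of power is a separate and lesser one. This follows from the design as written and depends on no assumed rate; the complication rates above are illustrative only.

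The error lies in the aims and the stated limitation, not in the analysis. It is confined to the first secondary objective and the preliminary outcome evaluation in section 3. Conclusions on recruitment, compliance and acceptability are unaffected. The change should be made, because the protocol nowhere states the limitation that matters most for interpreting its own outcomes.

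**What to change.** Reword five places:

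1. **Section 4.2, first bullet:** *To describe post-operative outcomes after prehabilitation, separately in donors and recipients, to inform the design of a comparative trial.*
2. **Section 3, the whole sentence on power:** *The study has no untreated comparator and is not powered; analysis will describe uncontrolled change from baseline in grip strength and wearable measures, and will describe post-operative outcomes in donors and in recipients.* In the same section, delete *improved* before the post-operative outcomes in the fourth key area.
3. **Section 7, the sentence saying that benefit may be shown:** *This study will describe outcomes in recipients and donors after prehabilitation. The absence of a comparator, not only lack of power, prevents attributing post-operative outcomes to prehabilitation.*
4. **Section 2, first sentence:** make feasibility, rather than effectiveness, the thing investigated.
5. **Section 5, opening sentence:** call the study uncontrolled, and replace *impact* with *feasibility*.

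The descriptive analysis in section 9.11 need not change. If the sponsor wants to keep the causal question, the protocol would have to name a comparator and a source for its data, which is a larger change.

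The rewording needs no extra patients, visits or data fields. Because an objective changes, it needs an amendment under the approvals in section 13.1. What is given up is a claim of benefit that the design cannot support.

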## **5) STUDY DESIGN & PROTOCOL**

This is a prospective study investigating the impact of prehabilitation in live kidney donors and their recipients.

### **Duration**

Initially, the study will recruit patients over a 9-month period, or until all 10 live donor pairs (20 participants) have been recruited. During this time, participants will wear a wearable smart device (Oura ring, Withings watch or Corsano wristband) for 2 weeks to collect baseline data before engaging with a prehabilitation programme for 6 weeks. The devices will be worn for a further 6 weeks after surgery, leading to participants being involved for a total 14-week period. Finally, a 3-month period will follow the completion of data collection when data analysis and write up will be completed.

## 5.1 Participants

The study aims to recruit a minimum of 20, maximum of 40 participants, half of whom will be live donors for renal transplantation and half of whom will be the recipients of the live kidney transplant.

## 5.2 Study Intervention and/or Procedures

Potential participants will be identified for by the renal transplant team in preoperative outpatient clinic. They will be provided with all information about the study in a participant information sheet and highlighted to the research team following completion of a consent to contact form.

Interested participants will then be contacted by a member of the research team, no sooner than 24 hours later. If the potential participant is deemed suitable following telephone screening, and would like to enrol in the study, they will be invited to a face-to-face meeting with a member of the research team. This meeting will take place in The Wearables Lab, Manchester Royal Infirmary. The participant will complete the consent form. The participant will then need to go through the baseline exercise questionnaire and circadian rhythm questionnaire. The participant will be sized and given a wearable device to use. Sizing, comfort, and stock availability of the different devices will determine which device the participant receives. The participant will be given manufacturer's instructions on the use of the wearable device (instructions in the box), charging it and when it is required to remove the device, for example devices are not MRI compatible. The participant will complete a hand grip strength test, which is a surrogate measurement for sarcopenia and important marker of frailty, measurements will be interpreted using both the International and European guidance on sarcopenia (24–26). They will then be instructed as to which exercise videos they should follow as part of their prehabilitation programme. The participant will be shown how to access the videos, how often they should use the video and given a folder of paper surveys and blank notebook to keep a 'patient journal.'

The participant will wear their chosen device for 2 weeks before starting the prehabilitation programme to allow for the collection of baseline data. On starting their programme, the participant will be asked to complete their exercise videos at least four times a week. After each time, the participant will complete a short paper-based survey of how they feel and their interaction with the video. Participants are encouraged to keep a patient journal on their thoughts/feeling during this study. Every 2 weeks a member of the research team will contact the participant by phone. This is to provide encouragement for their interaction with the study and any feedback from their device data. The participant may be instructed at this point to use a higher or lower intensity exercise video.

On admission for surgery, a member of the research team will visit the patient pre-operatively on the ward. Participants will submit their paper post-exercise surveys at this time. The participant will repeat the hand grip strength test and complete an end of prehabilitation questionnaire. The participant will remove their device during their inpatient stay.

On discharge from hospital the patient will reapply their wearable device until their 6 week follow up appointment. At this point they will return their device, any outstanding surveys, and complete the final questionnaire.

**Study Overview:**

Study enrolment, consent, setting up with wearable device and exercise assessment. 2 weeks wearing device to collect baseline data.

6 weeks of prehabilitation whilst wearing their device. Contact from the research team every 2 weeks to update on the prehabilitation programme.

Live kidney transplantation, either as a donor or a recipient. Device is removed for surgery. End of prehabilitation programme questionnaire.

Discharge from hospital. Wearable is worn again for the next 6 weeks during recovery.

6 week follow up. Wearable device given back and end of study questionnaire completed.

End of study

### 5.3 Prehabilitation exercise program

#### Oura Ring

The Oura ring is a commercially available wearable device. On enrolment to the study the research team will size and provide details on the ring to the participant. This includes how to use the ring and incidences when it should be removed. The participant will be asked to download the OURA ring app to their smart device so that the ring is able to upload its information.

**Withings Watch**

The Withings watch is a commercially available wearable device. On enrolment to the study the research team will provide details on the watch to the participant. This includes how to use it and incidences when it should be removed. The participant will be asked to download the Withings Health Mate app to their smart device so that the watch is able to upload its information.

**Corsano Wristband**

The Corsano wristband is an FDA approved; CE marked wearable wrist device. On enrolment to the study the research team will provide details on the wristband to the participant. This includes how to use it and incidences when it should be removed. The participant will be asked to download the Corsano Research app to their smart device so that the wristband is able to upload its information.

Data from all device applications is uploaded to the Cloud via Wi-Fi. Biometric data (heart rate, heart rate variability, respiratory rate, blood pressure, SpO2, core body temperature), activity data (step and workout count) and sleep data from the wearable devices will be extracted from the Cloud by a member of the research team. This will be stored on encrypted NHS Trust computers. Some of the information is available to participants through the relevant app. Should any of this be of concern to the participant they will be able to share this with their primary care team. A letter will be sent to each participant's primary care physician on enrolment to the study.

